Self-affirmation intervention for people newly diagnosed with advanced cancer:
A preliminary efficacy trial

NCT 05235750

March 27, 2024

Title: Self-affirmation intervention for people newly diagnosed with advanced cancer: A preliminary efficacy trial

PI: [name]

Study Title: Self-affirmation intervention for people newly diagnosed with advanced cancer: A preliminary efficacy trial

Principal Investigator: [name]
College of Integrated Clinical Enterprise SUSL Surgical Specialties
University of Arkansas for Medical Sciences
[name]
[name]

Email: [contact]

Study location: Winthrop P. Rockefeller Cancer Institute
[name]
[name]

Arkansas Hospice
[name]
[name]

Title: Self-affirmation intervention for people newly diagnosed with advanced cancer: A preliminary efficacy trial

PI: [name]

Hypothesis and/or Specific Aims or Objectives

The **primary aim** of this study is to explore the effects of self-affirmation via writing on patients newly diagnosed with advanced cancer, calculate effect sizes of the outcome variables, and estimate the appropriate sample size for the main study.

The **secondary aim** is to test the validity of the functional assessment of chronic illness therapy- spiritual well-being 12 item scale (FACIT-Sp-12), in its current (**Appendix A**) and revised forms (**Appendix B**).

It is hypothesized that: self-affirmation at the time following a diagnosis of an advanced cancer by affirming values or beliefs that are salient to self will help patients enhance self-esteem, reinforce spiritual well-being, decrease levels of anxiety or depression, and improve quality of life (QoL).

Study Design and Procedures

A single group time series study design will be employed (**Figure 1**).

[figure not shown]

Figure 1: Timeline for the four data collection points

The intervention Participants will be asked to write as guided by the researcher starting from Time 2 (two weeks post-baseline) for 4 weeks.

Specific criteria on the writing task:

- 1) write with a focus on affirming one's fundamental values and beliefs,
- 2) write in connection with one's cancer diagnosis, and
- 3) write at least once for a minimum of 20 minutes per week for four weeks.

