We will do everything we can to protect participants' privacy. Research data (including writings, if turned in) will be collected in a private place and stored in password-protected database that is held on a UAMS secure server. All hard copies of questionnaires and forms will be filed in locked file cabinets at a locked office. By signing the consent form, participants authorize the researcher to use the de-identified data for current and future data analyses.

A study number (or code) rather than the subject's name will be used on study records and databases for each study participant enrolled. The key that links the study numbers to the subjects will be securely stored in a password-protected database that is held on a UAMS secure server. All the data collected from participants will be strictly maintained as private and confidential throughout the entire study period and after the completion of the data analyses. Participants' names and other facts that might point to the patients will not appear in any presentation or publications. When the results are published or discussed in conferences, no information will be included that reveals research subjects' identity.

At the conclusion of the study, the data will be retained and later destroyed in accordance with institutional policy. The anticipated future use of the data may include secondary analysis of the writings from the participants, qualitative as well as quantitative. The key linking identifiers to the study numbers (or codes) will be destroyed after all the data analyses are completed.

Title: Self-affirmation intervention for people newly diagnosed with advanced cancer: A preliminary efficacy trial

PI: [name]

Data Analysis

Specific Aim 1.

a. Intervention fidelity and feedback from the participants

Fidelity of treatment in outcome research requires assessment and confirmation of the implementation of the independent variable as well as careful definition and operationalization of the intervention (Moncher & Prinz, 1991). For the purpose of this study, evidence of treatment fidelity will be assessed in the following aspects: 1) whether writing occurred at least once and (if so,) lasted for a minimum of 20 minutes each week, 2) whether writing was connected with the cancer diagnosis, and finally 3) whether writing focused on affirming one's fundamental values and beliefs.

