Due to the exploratory nature of the pilot study, both the variables to be explored (that is, allowed to vary and without definitions) and the intervention parameters to be controlled (as specified above) will be collected in a checklist of the implementation of the intervention (Appendix F). Specifically, the participants' feedback on the start time, duration, frequency, the topic of the writing, helpfulness of the study as well as the potential improvement in design), will be requested along with their response to questions concerning the evidence of treatment implementation (including whether writing occurred, whether the minimum amount of writing duration/frequency, and the prescribed focus of the writing as well as the relevance to cancer diagnosis were met).

b. Explore the intervention effects, calculate effect sizes of the outcome variables, and estimate the appropriate sample size for the main study.

Mean changes in patients' self-esteem, spiritual well-being (at the scale and factor levels), anxiety and depressive symptoms as well as QOL (global, total score and each subscale) will be evaluated using regression models for longitudinal data (i.e., repeated measures analysis of variance). The importance ratings for each subscale of the FACT-G and the FACIT-Sp-12 will be collected during each data collection meeting to aid interpretation of the intervention effect. Perceived threat at baseline and disease progression at each follow-up data collection meeting will be analyzed as moderators for exploratory analysis; psychosocial counseling or other supportive therapy/service/treatment received will be included as covariates. SAS® software will be used to perform all the proposed analyses. For hypothesis testing, an alpha (α) of 0.05 will be selected.

The standardized mean difference (Cohen's d statistic), or effect size will be computed by dividing the mean change by the standard deviation (SD) at the baseline (Kazis et al., 1989). In addition, raw score changes from baseline to follow-up will be assessed to interpret the clinical significance of the change by comparing with the established estimates of the minimal clinically important difference (MCID) (Jaeschke et al., 1989) for

Title: Self-affirmation intervention for people newly diagnosed with advanced cancer: A preliminary efficacy trial

PI: [name]

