Checklist for the intervention implementation

1. How frequently did you write?

_____ times per week

2. How long on average did you write each time?

_____ minutes each time

3. In a few words, please indicate what your writings focused on:

4. Did you find the process putting thoughts to writing helpful?

very helpful somewhat helpful not sure not very helpful

4a. If helpful, how did it help?

4b. If not helpful, what makes you think so?

5. Do you think the timing of the writing as arranged in this study appropriate?

5a. Would it have helped more if you were able to write earlier?

6. How much do you think writing is helpful for you to affirm or recall important values in your life?

very helpful somewhat helpful not sure not very helpful

7. Do you have any recommendation for how to make this writing intervention stronger?

Demographic Form

Below are some basic questions that are related to this study. We appreciate you answer them to the best of your knowledge. Please write down your responses or circle answers that fit.

1. What is your sex/gender? Male Female

2. What is your Age? _____

3. What is the date that you were informed of the diagnosis? _____

4. Are you Hispanic or Latino? No Yes

5. What is your race? _____ (White, African American, Asian, American Indian, Other)

6. What is your current marital/relationship status? (single/never married, married, divorced, widowed)

7. What is your highest grade of school completed (up to 8th grade, high school, college, graduate school)

8. What is your religious affiliation? (None, Protestant, Catholic, Jewish, Muslim, Other)
8a. Do you practice your religion? (no, occasionally, about weekly, daily)
8b. Do you think being spiritual must have a religious affiliation to associate? No Yes

9. Do you prefer to talk about your cancer diagnosis with others, or *not* to talk? _____ (no/yes/not sure)

10. Have you received or are seeking psychosocial counseling or other supportive therapy/service/treatment?
 No Yes

11. Have you ever put thoughts in your diary during stressful time in life? _____ (no/yes)

12. Would you please indicate your preference for filling out questionnaires in this study?
 paper and pencil iPad tablet read aloud by the investigator other (please specify)

Exit Survey

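### The Appendix F checklist never asks about the link to the cancer diagnosis and cannot confirm the weekly writing minimum, so the planned fidelity assessment cannot be delivered

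*Combined protocol and SAP*

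**What the plan says.** Study Design and Procedures sets three conditions for the writing task. The condition on amount is to "write at least once for a minimum of 20 minutes per week for four weeks"; the others are a focus on fundamental values and beliefs, and a connection with the diagnosis.

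Data Analysis, Specific Aim 1a, turns these into fidelity criteria:

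1. writing took place at least once and "lasted for a minimum of 20 minutes each week";
2. "whether writing was connected with the cancer diagnosis";
3. the writing focused on affirming fundamental values and beliefs.

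The same section says Appendix F will collect this evidence, through questions on "whether the minimum amount of writing duration/frequency" and on whether "the prescribed focus of the writing as well as the relevance to cancer diagnosis were met". Table 1 schedules the checklist at the 6-week and 8-week meetings.

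The Appendix F items that bear on fidelity are item 1 ("How frequently did you write", one blank for times per week), item 2 ("How long on average did you write each time", one blank for minutes), item 3 ("In a few words, please indicate what your writings focused on", open text) and item 6 (a helpfulness rating for affirming or recalling important values). The rest ask for feedback on helpfulness, timing and possible improvements.

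**The concern.** The analysis section promises evidence that the form does not collect. Criterion 2 has no question, and criterion 1 is defined week by week but recorded as a single summary. A participant's status on either criterion would have to be inferred or left unknown.

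In a single-group pilot, fidelity data are what tell the team whether any change, or lack of change, followed the intervention as prescribed. The plan places this assessment under Aim 1. If the form is used as printed, the report cannot say how many participants met criteria 1 and 2.

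**Working it through.** No figure in the plan needs reproducing. The check sets the criteria against the form, then tests what items 1 and 2 can show.

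**Form against criteria.** Appendix F contains questions 1, 2, 3, 4, 4a, 4b, 5, 5a, 6 and 7, ten in all. Those mentioning cancer or the diagnosis: 0 of 10. The numbering is continuous up to the Demographic Form, so this does not look like lost text.

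| Criterion | Bearing items | What they give |
|---|---|---|
| 1. Amount, each week | 1, 2 | One weekly frequency and one average length |
| 2. Link to diagnosis | None direct; 3 if volunteered | A mention is informative; silence cannot be scored |
| 3. Focus on values and beliefs | 3, 6 | Open text and a helpfulness rating; indirect |

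**What items 1 and 2 can show.** Suppose the respondent averages over the four weeks. Then item 1 = total sessions / 4, and item 2 = total minutes / total sessions.

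- One 20-minute session in each week: 4/4 = 1 per week, 80/4 = 20 minutes. Minimum met in 4 of 4 weeks.
- Four 20-minute sessions in week 1, none later: 4/4 = 1 per week, 80/4 = 20 minutes. Met in 1 of 4 weeks.
- One session a week of 35, 15, 15 and 15 minutes: 4/4 = 1 per week, (35 + 15 + 15 + 15)/4 = 20 minutes. Met in 1 of 4 weeks.

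The third pattern gives the same entries even if item 1 is read as a usual weekly rate, so the problem does not depend on averaging the frequency.

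Some failures are visible. Fewer than four sessions in total leave at least one week empty. Four sessions averaging under 20 minutes total under 80 minutes, so at least one week falls short.

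**Ambiguity in the minimum.** Two 10-minute sessions every week satisfy a weekly-total reading (2 x 10 = 20) and fail a single-session reading. The documents do not say which is meant.

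**Timing.** If the +/- 3 day windows are counted from baseline, Time 2 falls on days 11 to 17 and the 6-week meeting on days 39 to 45. The interval is then 39 - 17 = 22 to 45 - 11 = 34 days, against 4 x 7 = 28 days of writing. The 6-week checklist can therefore precede the end of the fourth writing week.

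**The case against.** The strongest reply is that little depends on this. The primary aim names effects, effect sizes and a sample size for the main study. Fidelity enters no model, covariate, subgroup or exclusion, so the loss is a weaker descriptive statement in an exploratory pilot. That correctly bounds the consequence, but it does not make the stated assessment deliverable.

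A second reply is that respondents will naturally report a usual week, so that three 40-minute sessions a week, say, would be reasonable self-report evidence of adherence. It would be, but it is not confirmation for each week, because an average length can hide short weeks. A retrospective grid also carries recall error; its advantage is that it asks the question the criterion poses.

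Third, item 3 may reveal a link to the diagnosis without prompting the approved answer. This is a real merit of open text, and item 3 should stay. It still leaves silence unscorable.

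Fourth, writings submitted through the portal or in notebooks could be examined. They could inform criteria 2 and 3 for those who share them, but Study Design and Procedures makes sharing optional and the plan names no such source for fidelity. That evidence would be partial and self-selected.

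Finally, the plan says start time will be recorded, yet Appendix F has no item for it. That is true. Because writing is stated to begin at Time 2, a week 1 to 4 grid still has an anchor.

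**Conclusion.** The concern holds. Of the three fidelity criteria, one has no question, one is recorded only as averages, and one is covered indirectly. The Aim 1a assessment cannot be produced as described.

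The finding on criterion 2 follows directly from the text and needs no assumption. For criterion 1, the example with all sessions in week 1 assumes averaging over four weeks; the example with unequal session lengths does not.

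The defect should be corrected but does not invalidate the trial. Outcome tests and sample size are untouched, and the limits of a single-group design remain either way.

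**What to change.** Revise Appendix F and the matching text under Specific Aim 1a.

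- **Amount.** Add a grid for writing weeks 1 to 4 (wrote or not, minutes), counted from Time 2 and completed at the 6-week meeting. If that meeting falls before the fourth week ends, complete the last row at the 8-week meeting, where the checklist is already scheduled. State whether the 20 minutes applies to one session or to the weekly total, and record minutes to match.
- **Content.** Add one direct question on connection with the diagnosis and one on focus on fundamental values and beliefs. Keep item 3.
- **Reporting.** Report the three criteria separately, without a new composite. Confidence intervals for the proportions are optional and do not bear on the defect. For participants assessed on the present form, state that criterion 2 was not directly asked and that criterion 1 is known only as an average.

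The cost is an amendment to one page and a few more minutes at existing meetings (an assumption, since the documents give no timing), for patients whose questionnaire burden is already acknowledged under Risks and Benefits. The grid is open to recall error over four weeks. Direct questions from the team that gave the writing instructions invite agreeable answers. A diary issued at Time 2 would reduce recall error but could itself prompt writing, so it is not proposed.

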To ensure that participants understand the nature and essence of the intervention, each patient will receive a page of writing instructions and a brief educational/informational session with the principal investigator (PI), both of which occur at two weeks post-baseline (Time 2 or T2); the writing instructions clarify the key expectations for the participants with respect to the writing intervention (in line with the criteria above) followed by examples to address what self-affirmation writing is and is not for this intervention.

Title: Self-affirmation intervention for people newly diagnosed with advanced cancer: A preliminary efficacy trial

PI: [name]

Both an online portal and notebooks for drafting and submitting the writings will be created for participants; patients may choose either approach to perform the writing task. At the end of the study period (or any other point), participants have the option to share their writings with the PI. However, given the high privacy nature of the content, sharing writings with the researchers is not required (which will be clarified with the participants) in order to encourage writing without reservation.

Study Population

The targeted participants are adult patients (age 18 or older) newly diagnosed with advanced cancer, and the total number of subjects to be enrolled will be a minimum of 50. This sample size is chosen based on an estimated effect size of 0.4-0.5 to test differences between paired observations in one sample, with α 0.05 and power 0.80 (Cohen, 1988).

The sample size estimate is tentative given the exploratory nature of this pilot study as the actual attrition rate as well as effect size may not be accurately predicted due to the high variability as found in the literature (Bai, 2021).

Recruitment Strategy

Patient recruitment for this pilot study will take place at two study sites: the Winthrop P. Rockefeller Cancer Institute at the University of Arkansas for Medical Sciences (UAMS) and the Arkansas Hospice.

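### Repeated measures ANOVA is named for every Aim 1 outcome with no missing-data rule; in its classical layout it omits patients with a missed visit and does not readily take the visit-level moderator

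*Combined protocol and SAP*

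**What the plan says.** One sentence in Data Analysis, Specific Aim 1, part b, sets the model for self-esteem, spiritual well-being, anxiety and depression, and quality of life: "regression models for longitudinal data (i.e., repeated measures analysis of variance". The abbreviation i.e. equates the two terms; it does not offer the second as an example. On implementation the section adds only "SAS® software will be used to perform all the proposed analyses" and "For hypothesis testing, an alpha (α) of 0.05 will be selected". The same paragraph states that "disease progression at each follow-up data collection meeting will be analyzed as moderators" in an exploratory analysis, and that supportive therapy received will be a covariate.

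The design is described as "A single group time series study design will be employed", with visits at baseline and at 2, 6 and 8 weeks (Table 1). On size, Study Population says "the total number of subjects to be enrolled will be a minimum of 50", based on an "estimated effect size of 0.4-0.5 to test differences between paired observations in one sample, with α 0.05 and power 0.80". It calls this tentative because "the actual attrition rate as well as effect size may not be accurately predicted". The Measures section provides for recording losses to follow-up and their reasons. No section states a complete-case rule, an available-data rule, imputation or a sensitivity analysis.

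**The concern.** The label covers two different analyses. The classical layout holds one row per patient with four outcome columns, and it deletes the row if any column is empty. A likelihood-based repeated measures model holds one row per visit and keeps whatever was observed. Two analysts following the text could therefore analyse different patients and report different effect sizes.

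The population is newly diagnosed with advanced cancer, and one of the two recruiting sites is a hospice organization, so missed visits are likely. The effect sizes are the main product of Aim 1 and are meant to size the next study. A loss of precision, or a shift toward patients well enough to finish, would carry into that calculation.

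There is also a difficulty that does not depend on dropout. Disease progression is collected at three follow-up visits, and the classical layout does not readily accept a moderator that changes by visit.

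**Working it through.** **1. The plan's own figure.** For a paired mean, n = ((z for 1 − α/2 + z for power)/d)², with α 0.05 and power 0.80 from Study Population. Two-sided, d = 0.4: (1.960 + 0.842)²/0.16 = 49.1, so 50. The exact noncentral t gives 52, and power at n = 50 is 0.79. At d = 0.5 the formula gives 7.851/0.25 = 31.4, so 32 (exact 34), and power at n = 50 is 0.93. The stated 50 is thus the two-sided figure for d = 0.4, with no allowance for loss. Sidedness is not stated; one-sided at d = 0.4 would need 39.

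**2. Assumed inputs.** The documents give neither an attrition rate nor a correlation between visits. I assume completely random loss at rate q per follow-up visit, q = 7% to 15%, and a correlation of 0.84 per two weeks that decays with the gap. Loss is either permanent dropout or isolated missed visits.

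**3. Complete cases.** All three follow-ups must be present: 50 × (1 − q)³.
- q = 7%: 50 × 0.93³ = 40.2
- q = 15%: 50 × 0.85³ = 30.7

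**4. Completer variance of the change from visit 2 to visit 3 (weeks 2 to 6).** The correlation over four weeks is 0.84² = 0.7056. In units of outcome SD², the variance per patient is 2 × (1 − 0.7056) = 0.5888. Dividing by the number of completers gives 0.01464 (q = 7%) and 0.01918 (q = 15%).

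**5. Likelihood variance.** For each missingness pattern, take the expected number of patients times the inverse covariance of the visits observed. Sum over patterns, invert, and apply the contrast (0, −1, 1, 0). The covariance is treated as known, which slightly favours the likelihood model.

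| Loss per visit | Type of loss | Completers | Likelihood | Ratio |
|---|---|---|---|---|
| 7% | permanent | 0.01464 | 0.01338 | 1.09 |
| 15% | permanent | 0.01918 | 0.01572 | 1.22 |
| 7% | isolated | 0.01464 | 0.01249 | 1.17 |
| 15% | isolated | 0.01918 | 0.01355 | 1.42 |

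Taking square roots, completer standard errors are about 5% to 10% larger with permanent dropout and 8% to 19% larger with isolated missed visits.

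**6. Covariates against Table 1.** Disease progression is scheduled at visits 2, 3 and 4 and has no baseline entry. Entered uncoded in a visit-level model, it would remove the baseline rows. Support received is asked only in item 10 of the Demographic Form, which Table 1 schedules at baseline alone.

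**The case against.** The strongest reply is that nothing in the plan says a patient is dropped. The leading phrase refers to longitudinal regression, no SAS procedure is named, and the label is also used for models fitted in PROC MIXED. A moderator measured at each follow-up even suggests that such a model is intended. This stands: a reader might infer that the plan adopts a complete-case analysis, and the documents do not say so. But neither do they exclude it, and the named method in its classical form leads there.

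A reader might also blame the model for the whole fall in paired power at d = 0.4, from 0.79 with 50 patients to 0.69 with 40 and 0.56 with 30. That is not supported. Most of the fall is unobserved data that no model restores. Under the assumptions above with permanent dropout, completer against likelihood power is about 0.70 against 0.74 at 7% loss and 0.57 against 0.66 at 15%, so model choice accounts for about 0.04 to 0.09. With isolated missed visits it accounts for about 0.07 to 0.16. The effect scale matters too: a change of 0.4 outcome SD at correlation 0.7056 is a paired d of 0.4/√0.5888 = 0.52. At paired d = 0.5, 34 complete cases suffice.

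Criticism of the covariance assumption carries little weight. The classical SAS layout also gives multivariate and sphericity-corrected tests, and unequal spacing is harmless when visit is categorical.

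Finally, the plan limits missed visits through convenient scheduling and rescheduling, payment at each meeting, and exclusion of patients too ill to take part. That may keep loss low, but it does not say how the remaining loss is analysed.

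**Conclusion.** The point holds as a choice of method that should be replaced. It does not show that patients will be discarded. The text equates its model with repeated measures ANOVA and gives no missing-data rule. Read classically, that analysis omits partial records and fits poorly with the plan's own visit-level moderator.

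The avoidable cost is a variance inflation of 1.09 to 1.22 (permanent dropout) or 1.17 to 1.42 (isolated missed visits) for the change from visit 2 to visit 3. This rests on assumed random loss of 7% to 15% per visit and a correlation of 0.84 per two weeks, and would shrink with lower loss.

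If dropout depends on earlier scores, completer effect sizes may also be biased. A reader might want a figure for that bias, but its direction and size cannot be derived from the documents. The study is an exploratory pilot and stays feasible either way. The change should be made because the effect sizes will be used to size the main study.

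**What to change.** In Data Analysis, Specific Aim 1, part b, replace the parenthesis naming repeated measures ANOVA with a likelihood-based linear mixed model for repeated measures in SAS:

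- REML, visit as a categorical factor, unstructured within-patient covariance and Kenward-Roger degrees of freedom.
- All available visits from all enrolled patients, with missing at random stated as the assumption. A short sensitivity analysis for informative dropout would be a sensible addition.
- The plan's changes, including baseline to follow-up, estimated as visit contrasts, so that the quantities of interest stay as they are.
- Support received entered as a baseline covariate, unless it is also recorded by visit.
- Disease progression kept as an exploratory visit-level moderator, with a coding rule that retains the baseline rows.
- A simpler covariance structure named in advance as fallback, since an unstructured model may not converge with about 50 patients.

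The cost is a few sentences and different SAS code. No extra patients are needed, and no extra data unless the sponsor chooses to record support received by visit.
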